5.9 Statistical Analysis

5.9.1 Sample Size

Based on delirium episodes in the feasibility study, a minimum of 50 consecutive patient records are required (from each site, at each timepoint) to identify each sample of 30 delirium episodes. This figure will be revisited during the internal pilot.

The study requires 30 inpatients with a delirium episode from each of 20 PCUs

Size of cluster=30

Number of PCU clusters for randomisation=20

Total number of inpatient records required = 2000

Number of delirium episodes inpatient records required = 1200

Intraclass correlation coefficient (ICC) is generally smaller for clinical outcomes than for process outcomes, with a median value of 0.03. Our goal is to achieve 12% reduction (from 70% to 58%), leading to a moderate effect size of 0.4. No attrition rate is expected since each PCU will collect data from cross sectional cohorts (baseline and follow-up). The outlined sample size will provide 92.3% power to detect a 12% reduction of proportion of days affected by delirium, at 0.05 significance level, assuming an ICC of 0.03.

5.9.2 Planned recruitment rate

An internal pilot will be implemented for months 10-15 with provisional stop/go criteria (see appendix A) to be further developed and approved by the funder by May 2025.

Stop criteria equates to 0 site or records being recruited within this period. A warning criterion will be for if <10 site/records are recruited during this period. Go criteria will be for if ≥ 10 sites/records are recruited during this period. The stop/go will be reviewed by the TSC. There may be a funder requirement to close the study prematurely if recruitment does not achieve the Stop-Go targets.

5.9.3 Data Analysis

We will follow the CONSORT extension to cluster randomised trials⁴⁷ for analysis and reporting. Primary analyses will be conducted on intention-to-treat basis and follow a prespecified statistical analysis plan, overseen by Trial Steering Committee. Patient baseline demographics will be summarised for each group with descriptive statistics. Primary outcome (proportion of PCU inpatient delirium days) will be analysed by two level modelling with PCU as cluster, adjusting for intervention arms and stratification factors. We will also report the primary outcome by deceased/discharged patients and undertake a sub-group analysis via two-level modelling approach. A patient who dies shortly after admission has a shorter inpatient stay than a patient who is discharged. Additionally, the risk of delirium is greater in those closer to death. Drawing from our feasibility study data, we expect the deceased and

discharged patients in a 2:1 ratio. This assumption will be checked during the internal pilot and any natural variation in this ratio will be accounted for in a sub-group sensitivity analysis.

Additionally, we will collect the dates of hospital admission, first delirium and mortality (if applicable) for all participants. This data will be used to form the time to first delirium (in days) as a key secondary outcome, which competes with patient death. A competing risk analysis will be undertaken accordingly.

For other secondary outcomes, routinely assessed symptom burden and functional status (IPOS and AKPS) will be reported by intervention arms at each time-point. To evidence the guideline-adherence of delirium care processes, we will report on the process outcomes related to delirium early detection, delirium care and symptom distress, including the use of 4AT screening tool, presence/absence of delirium risk assessment, use of RASS-Pal, clinician-documented diagnosis of delirium, clinician assessment of cause/reversibility, presence/absence of delirium care plan, use of antipsychotics in relation to documented harmful/distressing behaviour towards self or others. For each PCU cluster, the proportion of patients with delirium will be summarised by intervention arms at each time-point. The linked Hospital Episode Statistics (HES) data will be summarised and used for health economic analysis.

6 Health Economic Evaluation (WP2b)

We will conduct a cost-effectiveness analysis (CEA) from the health system perspective using a lifetime horizon. The main source of data for the CEA will be the cRCT, supplemented with routine data and the published literature. To gain as much detail as possible to best inform the health economic evaluation, we will not stop the study early should one cRCT arm have clear emerging superiority.

6.1 Data collection

Following DARs approval, we will estimate costs (payer perspective) in two settings: PCU (via routine data) and acute hospital (via linked HES data), with all data housed and analysed exclusively in the University of Hull's Data Safe Haven. We will estimate the cost of a day in PCU, stratified by PCU type, using Personal Social Services Research Unit (PSSRU) data, differentiating between staffing costs for patients with and without delirium, based on staff logs and discussions with clinicians and managers.

We will identify acute hospital admissions via linked HES data and estimate associated costs using reference costs adjusted for HRG code, co-occurring conditions including delirium, and length of stay. We will adjust for the additional cost associated with an acute hospital admission ending in death. We will estimate the resources associated with *CLECC-Pal Delirium* through review of staff activity and discussions with clinicians and managers.

Missing outcome data will be addressed by using multiple imputation by chained equations.

6.2 Data Analysis

We will estimate incremental effectiveness of the intervention using the primary outcome (Site PCU inpatient days affected by delirium). We have chosen cost-effectiveness analysis over cost-utility analysis in the context of practical and ethical challenges in primary data collection of generic health related quality of life (HRQoL) data in our population and study design. In secondary analyses, we will explore relationships between IPOS and AKPS scores with delirium and non-delirium days at sites where these data are collected, and explore the scope for using these in cost-effectiveness analyses, thus investigating if incorporating a wider set of HRQoL domains affects our interpretation and conclusions.

Prior to conducting primary analysis, we will examine: (i) baseline differences on characteristics associated with outcome and where necessary control for baseline variables in analysis; and (ii) skew, kurtosis and heteroscedasticity in the cost data and fit an appropriate (most likely, nonlinear) model. We will address missing outcome data using multiple imputation. We will bootstrap each set of regressions with 1000 replications and combine these bootstrapped results in estimating cost-effectiveness acceptability curves. If data characteristics require it, we will account for correlated costs and effects using seemingly unrelated regressions. Recognising the uncertainty associated specifically with a cRCT, we will employ a stratified two-stage nonparametric bootstrap resampling procedure for clustered data. We will use discount rates in line with NICE guidance at the time of analysis. For the purposes of cost-effective analyses, each day affected by delirium will be treated as a 'whole (24 hour) day'.

Data analysis will include:

- Estimation of the cost of a day in PCU, stratified by PCU type, using personal social services research unit (PSSRU) data, differentiating between staffing costs for patients with and without delirium, based on staff logs and discussions with clinicians and managers.
- Estimation of associated hospital admission costs using reference costs adjusted for HRG code, co-occurring conditions including delirium, and length of stay. We will adjust for the additional cost associated with an acute hospital admission ending in death.
- Estimation of the resources associated with the CLECC-Pal Delirium study intervention through review of staff activity and discussions with clinicians and managers.
- Estimation of incremental effectiveness of the intervention using the primary outcome (PCU inpatient days affected by delirium).

- Estimation of cost-effectiveness using IPOS and AKPS scores at those site PCUs where these data were collected, thus investigating if incorporating a wider set of HRQOL domains affects our interpretation and conclusions.

7. Process Evaluation (WP2c)

7.1 Fidelity

We will measure the percentage of eligible staff overall, and by type of staff, participating in the training for each of the ten PCUs introducing *CLECC-Pal Delirium*.

7.2 Interviews

The *CLECC-Pal Delirium* intervention is based on Normalisation Process Theory (NPT), a social-psychological theory of the inter-relationships between what people do, the context they do it in, and the extent to which interventions are ‘normalised’ (implemented) into routine practice.

The interview part of the process evaluation will begin a 6 month timepoint after commencing the study *CLECC-Pal Delirium* intervention at each PCU site. The process evaluation NPT’s four constructs will be used to structure data collection, analysis and interpretation for staff interviews. The constructs will enable understanding of key implementation challenges:

- coherence (do staff understand why *CLECC-Pal Delirium* it is being used?)
- cognitive participation (are staff engaged and committed to it?)
- collective action (are staff working together to use it?)
- reflexive monitoring (are staff appraising the consequences of using it?).

7.2.1 Sample size:

Four out of the ten intervention site PCUs will be selected for in-depth qualitative research. We will sample purposively based on: PCU type, PCU size, diversity of population served, and historical participation with interventional research. In each of the four site PCUs, we will interview 6-10 staff (total 24-40) and 6-10 inpatients and their informal carers (total 24-40).

7.2.2 Screening and approach

Each Site Principal Investigator (PI) will identify staff members who can be approached to participate in interviews with the research team, and inpatients and informal carers who can be approached to participate in interviews with the research team. The Site PI, in conjunction with relevant clinicians at their PCU, will assess whether patients have capacity to be approached about research, whether they need to be approached while their informal carer is present, and that they are no longer experiencing delirium. Inpatients and their family member/informal carer will be offered the option of telephone, virtual or in person interviews while the patient is staying in the PCU. Prior to interview, both the informal caregiver/and or the patient will be asked about their participation preferences. The informal carer and/or patient will be asked if they wish (i) the carer to join the patient interview to facilitate the patient's participation (ii) the carer join the patient interview to offer their own views about the care provided (iii) have separate interviews. They can select any or all of the three options. A Participant Information Sheet (PIS) will be provided to the staff member, inpatient and their informal carer prior to the interview by the site PI or suitably trained delegate. Translated Participant Information Sheets will be prepared if required, or staff members who can communicate in an inpatients' preferred language will approach patients and informal carers to facilitate inclusiveness of the recruitment process for inpatient/carers. For interviews, interpreters will be engaged where necessary.

7.2.3 Participant selection

The Site PI (or suitable delegated PCU staff member) will take informed consent from staff and inpatients/carers and contact details will be sent to the research team to secure HHTU study NHS email. After consenting inpatients/carers, PCU staff will promptly contact the HHTU team to schedule the HHTU researchers to come to the PCU to conduct the interviews of inpatients/carers. Interviews will be conducted with the inpatients/carers remotely, if preferred by participant.

When on site the HHTU researchers will review the completed consent forms for accuracy and completeness and will take the hard copies for secure storage at HHTU (ensuring copies remain at site).

The HHTU researchers will confirm with the PCU staff that no changes in capacity have occurred since consent was given prior to the interviews. When confirmed the PCU staff will help the HHTU researchers identify the correct PCU inpatients that have consented. For staff members that have consented to interview their details will be collected by the Site PI and emailed through to the HHTU research team. Consented staff members will be contacted remotely by the HHTU research team.

The research team will add the contact details and will upload the signed informed consent form to the secure web-based study database managed by HHTU.

Interviewees will be selected by the researcher to obtain maximum diversity of interviewees, that is, a range of type of staff roles and grades and a range of patients/families from different socio-economic backgrounds and ethnic groups.

Purposive sampling of inpatients will be undertaken to interview those who have experienced delirium and those who have not, as the intervention covers both prevention and management of delirium.

Not all those who have expressed an interest to be interviewed will be selected due to purposive sampling methodology.

Inpatients/Carers Inclusion Criteria:

- Inpatients with capacity to consent
- Carers of inpatients with capacity to consent

Inpatients/Carers Exclusion Criteria:

- Patients who do not have capacity at point of interview will be withdrawn
- Carers of inpatients without capacity to consent

Staff Inclusion Criteria

- PCU staff members with patient contact
- Member of PCU management or Executive

Staff Exclusion Criteria

-Staff without patient contact (not including managerial roles)

7.2.4 Informed Consent

Sufficient time will be given between the PIS and informed consent so that all questions can be answered by the Site PI in consultation with (where necessary) the process evaluation team.

7.2.5 Conduct of Interviews

Semi-structured interviews will be undertaken in the PCU. Every effort will be made to find a quiet and comfortable room to conduct the interview to maintain privacy as much as possible. All interviews will be recorded and transcribed.

Staff will be offered the option of telephone, virtual or in person interviews; interviews will be a maximum duration one hour. Interviews may be taken with frequent breaks to ensure that a patient is not fatigued by the process and will be stopped early if necessary or rearranged.

Palliative care patients who agree to participate in research can find the opportunity to discuss their situation helpful. However, there is potential that some patients and informal carers feel upset during the interview as a result of talking about their life circumstances, experiences of delirium, and the care they are receiving. The Qualitative Researcher undertaking the interviews will be an experienced palliative care researcher and will listen to patients and informal carers sensitively, and allow breaks or withdrawal from the interview if they wish. It will not be the Qualitative Researcher's role to offer any counselling but if the Qualitative Researcher is concerned about distress during or after the interview, with the interviewee's permission, the Qualitative Researcher will pass their concerns on to the PCU team. A study log will be kept of any instances where the Qualitative Researcher is made aware (by a participant, their family or the clinical team) of distress experienced around the time of conducting an interview. The anonymised log will be regularly monitored and action taken regarding the content, processes and/or conduct of interviews as appropriate. We shall also work with the PCUs to ensure that clear safeguarding policies and reporting mechanisms are in place.

The Qualitative Researcher may be distressed by the interviews. The Process Evaluation Lead will meet with the Qualitative Researcher regularly to debrief about their experiences and feelings. If there is anything that requires a clinical input, the Process Evaluation Lead will approach a senior clinical member of the research team for help ([name] or [name]).

Interviews with staff will explore mechanisms of action, implementation of the intervention within each PCU, how contextual issues affected implementation and outcomes, and fidelity. Interviews with patients and informal carers will explore how delirium was managed (if they experienced delirium) and their experiences of actions expected by PCUs to prevent delirium (these will be offered as prompts).

If the Qualitative Researcher identifies aspects of care that are concerning, these will be discussed with the Process Evaluation Lead and Chief Investigators before being raised with the Site PI, but will not be followed up.

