9.5 Safety Reporting

As the study intervention does not change the delivery of standard practice, no safety reporting is required. Any safety concerns from the site PCUs will be reported to HHTU and escalated to the CI, Sponsor and oversight committees where necessary.

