9.6 Serious Breaches

PIs and researchers are required to promptly notify the HHTU of a serious breach (as defined in the latest version of the National Research Ethics Service (NRES)).

A 'serious breach' is defined as a breach of the protocol or of the conditions or principles of GCP (or equivalent standards for conduct of non-CTIMPs) which is likely to affect to a significant degree the safety or physical or mental integrity of the trial subjects, or the scientific value of the research. In the event of doubt or for further information, the PI or researcher should contact the study Trial Manager at the HHTU.

Safety issues and queries can be raised at site to HHTU for assessment by the CI, Sponsor and oversight committees and for actions to be implemented where appropriate. Site teams are to be encouraged to raise concerns to ensure the intervention is being implemented accurately and ensure data integrity for the study endpoints is maintained. This is particularly important when the study sites are likely to be research naïve. Open dialogue between HHTU and the study site PCUs is encouraged throughout.

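### Section 7.2.5 rules out follow-up of concerning care found by the study's interviewer and is not tied to the escalation route in sections 9.5 and 9.6

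*Protocol*

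**What the plan says.** Section 7.2.5 deals with what the interviewer may come across. The trigger is "If the Qualitative Researcher identifies aspects of care that are concerning". The first step is that "these will be discussed with the Process Evaluation Lead and Chief Investigators". This happens "before being raised with the Site PI, but will not be followed up". Nothing comes after the Site PI.

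The same section handles two neighbouring matters differently. Distress around an interview is logged, and "The anonymised log will be regularly monitored and action taken regarding the content, processes and/or conduct of interviews as appropriate". There is also a general undertaking: "We shall also work with the PCUs to ensure that clear safeguarding policies and reporting mechanisms are in place".

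Safety concerns arising at the units have their own route. Section 9.5 states: "Any safety concerns from the site PCUs will be reported to HHTU and escalated to the CI, Sponsor and oversight committees where necessary". Section 9.6 adds: "Safety issues and queries can be raised at site to HHTU for assessment by the CI, Sponsor and oversight committees", with action to follow where appropriate. It also requires investigators and researchers to notify HHTU promptly of a serious breach.

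Section 9.4 puts participant safety within the TSC's remit. Section 9.3 promises a monitoring plan that looks for issues and trends across sites, with inpatient safeguarding as one of its purposes.

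**The concern.** The sentence in 7.2.5 is a positive rule, not a detail left to a later document. It ends the route at the Site PI and says that nothing further will be done. The Site PI belongs to the unit whose care is in question: section 7.2.2 describes "The Site PI, in conjunction with relevant clinicians at their PCU" as the people who judge whether a patient can be approached.

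Concerns about care are foreseeable in these interviews. Patients and carers are asked how delirium was managed, patients are offered interviews during their stay, and sampling deliberately includes people who have had delirium. A concern may therefore be about care still being given. Section 9.5 also waives routine safety reporting, so the interviews are one of the few occasions on which the study team hears directly from patients.

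At stake is whether a concern bearing on participant safety reaches the body charged with it, and whether similar concerns at different units could be seen together.

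**Working it through.** No plan figure depends on this point and there is nothing to recompute. The check sets the routes side by side.

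**Who raises the concern**
- 7.2.5: the study's interviewer. Section 7.2.3 shows that HHTU researchers conduct the interviews.
- 9.5: the site units.
- 9.6: for general safety issues, the site; for serious breaches, investigators and researchers.

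**What is covered**
- 7.2.5: any concerning aspect of care. This is wider than safety but includes it.
- 9.5 and the general part of 9.6: safety concerns and queries.
- 9.6, serious breach: a breach of the protocol or of good practice standards likely to affect, to a significant degree, participants' safety or integrity or the scientific value of the research.

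**Who is told**
- 7.2.5: Process Evaluation Lead, Chief Investigators, then the Site PI.
- 9.5: HHTU, then the Chief Investigator, Sponsor and oversight committees where necessary.
- 9.6: HHTU, with assessment by the same bodies for general safety issues.

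**What happens next**
- 7.2.5: follow-up is expressly ruled out. No record of the concern or of the unit's response is provided for.
- 9.5: escalation where necessary.
- 9.6: assessment, and action where appropriate.

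Section 9.5 names four recipients: HHTU, Chief Investigator, Sponsor and oversight committees. On the 7.2.5 route the Chief Investigators are named, and HHTU is present because its researchers do the interviewing. The Sponsor and the committees are not provided for.

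That leaves one class of event without a defined route onward: a safety concern found by the interviewer that is not a serious breach. Section 9.5 is not worded to take it in, the serious-breach duty does not reach it, and 7.2.5 stops it at the unit.

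**Exposure.** Section 7.2.1 selects four of the ten intervention units, with 6 to 10 staff in each (4 × 6 = 24 to 4 × 10 = 40) and 6 to 10 inpatients and their informal carers in each (again 24 to 40). Together that is 24 + 24 = 48 to 40 + 40 = 80 on the protocol's totals, and possibly more if carers are counted separately. This counts people interviewed. The protocol gives no basis for an expected number of concerns.

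**The case against.** The strongest reply is that the information does not stay inside the unit. HHTU researchers conduct the interviews and the Chief Investigators hear of the concern before the Site PI does. Section 9.11 gives the Chief Investigator overall responsibility for conduct, and HHTU manages the study on the Sponsor's behalf. Both sit on the Trial Management Group, whose members may report to the TSC. This stands, and it rules out saying that the Sponsor and TSC could never learn of a concern. It does not supply the missing step: escalation is possible, but 7.2.5 does not call for it and its closing words point the other way.

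A reader might infer that 7.2.5 flatly contradicts 9.5. The documents do not support that. Section 9.5 concerns matters coming from the units, 7.2.5 concerns matters noticed by an interviewer, and the scopes differ. The two could even run in sequence, with the Site PI passing a safety concern back to HHTU under 9.5. Nothing in 7.2.5 says so, however, and that sequence would depend on the unit concerned reporting itself.

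A reader might also infer that grave matters would be lost. The serious-breach duty in 9.6 binds researchers, and 7.2.5 does not switch it off.

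The no-follow-up words may only have been meant to say that researchers do not investigate clinical care themselves. That would be a reasonable position, but it is not what the sentence says, which is a reason to reword it. The safeguarding undertaking in 7.2.5 is a real mitigation, but it is general and does not override the specific rule.

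**Conclusion.** The point holds in limited form. Followed as written, 7.2.5 lets a patient-safety concern found by the study's interviewer, below the serious-breach threshold, stop at the unit concerned. It need not reach the TSC, and it need not be compared across sites as section 9.3 intends. The routes are unreconciled; they are not in strict contradiction.

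The size is modest. The gap applies to interviews in four units, HHTU and the Chief Investigators are aware of any concern, and serious breaches are covered elsewhere. The 48 to 80 interviewees should not be read as 48 to 80 concerns. There is no effect on sample size, power or the primary analysis. This is a matter of participant protection that a short change of wording would settle.

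The conclusion assumes that no other study document, such as the monitoring plan or an HHTU procedure, already links interviewer concerns to the 9.5 route. If one does, 7.2.5 should still be brought into line with it.

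**What to change.** In section 7.2.5, replace the words ruling out follow-up with two statements:

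1. The research team does not itself investigate or manage care, which remains with the unit.
2. A concern bearing on participant safety also enters the route in sections 9.5 and 9.6, going to the Chief Investigator, Sponsor and TSC where necessary.

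Record the concern and the site's response in HHTU's study monitoring records. The log of interview distress is not a suitable place: it is anonymised and exists to adjust how interviews are run, whereas the trending in section 9.3 needs the site to be known.

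A matching phrase in section 9.5, so that it covers concerns identified by study researchers as well as those from the units, would close the gap from both sides. None of this sets a clinical rule.

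The cost is about a paragraph of protocol text, a small amount of extra recording, and matching wording in the interview information sheet on when concerns are passed on.
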